9.4. Statistical Analyses

The SAP will be finalized before database lock and it will include a more technical and detailed description of the statistical analyses summarized in this section. This section is a summary of the planned statistical analyses of the most important endpoints, including primary and secondary endpoints.

9.4.1. General Considerations

Hypothesis testing will be used for the interim (Stage 1) and final (Stage 1 + Stage 2) analyses of the efficacy endpoint of ORR. No formal hypothesis testing will be used for any other endpoints or other study data, such as demographics and safety data.

Tabulations will be produced for appropriate disposition, demographic, baseline, efficacy, and safety parameters. For categorical variables, summary tabulations of the number and percentage of subjects within each category (with a category for missing data) of the parameter will be presented, as well as 2-sided 95% CIs, unless stated otherwise. For continuous variables, the number of subjects, mean, median, standard deviation, minimum, and maximum values will be presented. Time-to-event data will be summarized using Kaplan-Meier (KM) methodology using 25th, 50th (median), and 75th percentiles with associated 2-sided 95% CIs, as well as number and percentage of censored observations.

The Investigator's assessments of disease response will be used as the basis for the evaluation of the primary and secondary efficacy endpoints.

9.4.1.1. Procedures for Handling Missing, Unused, and Spurious Data

All available efficacy and safety data will be included in data listings and tabulations. In general, missing data will be treated as missing and no data imputation will be applied, unless otherwise specified. Data that are potentially spurious or erroneous will be examined according to standard data management operating procedures. Details of procedures for handling missing, unused, or spurious data can be found in the SAP.

9.4.2. Primary Endpoint Efficacy Analysis

ORR will be assessed according to RECIST v 1.1 ([Eisenhauer 2009](#)). Final analysis of the combined Stage 1 and Stage 2 ORR will occur after the last subject enrolled and dosed in Stage 2 has been followed for 6 months.

9.4.3. Secondary Efficacy Endpoints Analyses

- ORR will be assessed according to RECIST v 1.1 ([Eisenhauer 2009](#)). Evaluation of ORR in Stage 1 will occur after the last subject enrolled and dosed in Stage 1 has been followed through at least the first disease response assessment.
- DOR will be calculated for those subjects with a CR or PR from the time of first response to PD using KM methods
- PFS will be assessed using KM methods from time of first treatment to PD or death
- OS will be assessed using KM methods from time of first treatment to death

9.4.4. Primary Safety Endpoint Analysis: Stage 1

- Safety analyses will be performed on the ITT population, and safety endpoints will be tabulated and presented.
- AEs will be coded using the Medical Dictionary for Regulatory Activities (MedDRA) Version 20.0 or higher for purposes of summarization. All AEs occurring during the study will be included in by-subject data listings and tabulated by MedDRA system organ class and preferred term. Adverse events will be summarized overall, by relationship to each study intervention, and by severity. Events leading to death, SAEs, and events resulting in discontinuation of study interventions will be listed and, if warranted by the data, tabulated.
- AEs of special interest (AESI) will be defined for analysis purposes in the SAP and will be summarized using the methods as described in the above bullet.
- Exposure to duvelisib and pembrolizumab, including the proportion of expected doses received, will be tabulated.
- Changes from baseline over time for vital sign measurements (including diastolic and systolic blood pressure) will be summarized.
- Individual subject laboratory parameter values and changes from baseline over time will be summarized using descriptive statistics. Severity of select clinical laboratory measures will be determined using NCI CTCAE criteria and Grade 3 or 4 laboratory values will be presented in a separate table.

- The use of concomitant medications, coded using the World Health Organization Drug Dictionary, will be tabulated and included in a by-subject listing.

9.4.5. Secondary Safety Endpoint Analysis

Safety analyses, as described in Section 9.4.4, will be performed on the ITT population for Stage 1 and Stage 2 combined, and safety endpoints will be tabulated and presented.

9.4.6. Secondary PK Endpoints Analyses

- PK analyses will be conducted on the ITT population.
- Blood samples will be taken for the analyses of duvelisib and metabolite IPI-656 in plasma at the time points defined in the SoA (Table 2 and Table 4). PK exposure parameters (maximum observed concentration [C_{max}] and area under the curve [AUC]) will be determined using the bioanalytical data and Population PK (POPPK) modeling. The PK data will be summarized using descriptive statistics and will be listed and summarized in tabular and/or graphical form.
- Based on the exposure parameters determined from POPPK model, the relationship between duvelisib exposure and response and AEs will be analyzed.

9.4.7. Exploratory Endpoints Analyses

- Changes from baseline over time for ECOG performance status will be summarized. A by-subject listing of ECOG performance status data will be prepared.
- Pharmacodynamic analyses will be conducted on the ITT population for Stage 1.
- Pharmacodynamic and prognostic markers will be evaluated relative to baseline levels and change from baseline levels.
- Biomarker effects will be summarized using descriptive statistics; associations of biomarkers, including tumor and/or immune cell PD-L1 levels and HPV status, with clinical efficacy and/or safety outcomes may be explored.

9.5. Interim Analyses

An interim analysis of the primary endpoint will be conducted at the end of Stage 1 as part of the Simon two-stage design (Simon 1989).

9.6. Data Monitoring Committee

This study will not use a data monitoring committee.

10. SUPPORTING DOCUMENTATION AND OPERATIONAL CONSIDERATIONS: APPENDICES**Table 17: Appendices**

Appendix	Title	Section
1	RECIST Version 1.1	10.1
2	CYP3A Inhibitors, Inducers, and Substrates	10.2
3	Clinical Laboratory Tests	10.3
4	Contraceptive Guidance	10.4
5	ECOG Performance Status	10.5
6	Regulatory, Ethical, and Study Oversight Considerations	10.6
7	Abbreviations	10.7

10.1. Appendix 1: RECIST Version 1.1

(Modified from [Eisenhauer 2009](#))

All subjects will have their BEST RESPONSE on study classified as outlined below ([Table 18](#) and [Table 19](#)):

Complete Response (CR)

Disappearance of all target lesions. Any pathological lymph nodes (whether target or non-target) must have reduction in the short axis to < 10 mm.

Partial Response (PR)

At least a 30% decrease in the sum of diameters of target lesions, taking as reference the baseline sum diameters.

Stable Disease (SD)

Neither sufficient shrinkage to qualify for PR nor sufficient increase to qualify for PD, taking as reference the smallest sum diameters while on study.

Progressive Disease (PD)

At least a 20% increase in the sum of diameters of target lesions, taking as reference the smallest sum on study (this includes the baseline sum if that is the smallest on study). In addition to the relative increase of 20%, the sum must also demonstrate an absolute increase of at least 5 mm. The appearance of one or more new lesions will also be considered PD.

Response Duration

Response duration will be measured from the time that the measurement criteria for CR/PR (whichever is first recorded) are first met until the first date that recurrent or progressive disease is objectively documented, taking as reference for PD the smallest measurements recorded on study.

Stable Disease Duration

Stable disease duration will be measured from the time of start of the intervention until the criteria for progression are met, taking as reference the smallest sum of diameters recorded on study (if the baseline sum is the smallest, this is the reference for calculation of PD).

Table 18: Evaluation of Best Overall Response – Subject with Target (\pm Non-target) Disease

Target Lesions	Non-target Lesions	New Lesions	Overall Response
CR	CR	No	CR
CR	Non-CR/Non-PD	No	PR
CR	NE	No	PR
PR	Non-PD/or not all evaluated	No	PR
SD	Non-PD/or not all evaluated	No	SD
Not all evaluated	Non-PD	No	NE
PD	Any	Yes or No	PD
Any	PD	Yes or No	PD
Any	Any	Yes	PD

Abbreviations: CR: complete response; NE: inevaluable; PD: progressive disease; PR: partial response; SD: stable disease.

Table 19: Evaluation of Best Overall Response – Subject with Non-target Disease

Non-target Lesions	New Lesions	Overall Response
CR	No	CR
Non-CR/Non-PD	No	Non-CR/Non-PD ^a
Not all evaluated	No	NE
Uequivocal PD	Yes or No	PD
Any	Yes	PD

Abbreviations: CR: complete response; NE: inevaluable; PD: progressive disease.

^a “Non-CR/non-PD” is preferred over “stable disease” for non-target disease because SD is increasingly used as an endpoint for assessment of efficacy in some studies; therefore, to assign this category when no lesions can be measured is not advised.

Note: Subjects with a global deterioration of health status requiring discontinuation of intervention without objective evidence of PD at that time should be reported as “symptomatic deterioration.” Every effort should be made to document the objective progression even after discontinuation of study interventions.

Method of Assessment

The same method of assessment and the same technique should be used to characterize each identified and reported lesion at baseline and during follow-up.

Clinical Lesions

Clinical lesions will only be considered measurable when they are superficial and < 10 mm diameter as assessed using calipers (e.g., skin nodules). For the case of skin lesions, documentation by color photography including a ruler to estimate the size of the lesion is suggested.

Chest X-ray

A chest CT scan is preferred over a chest X-ray, particularly when progression is an important endpoint, since CT is more sensitive than X-ray, particularly in identifying new lesions. However, lesions on chest X-rays may be considered measurable if they are clearly defined and surrounded by aerated lung.

CT (preferred) or MRI Scans

CT is the best currently available and reproducible method to measure lesions selected for response assessment. Measurability of lesions on CT scan is defined based on the assumption that the CT slice thickness is 5 mm or less. When CT scans have a slice thickness > 5 mm, the minimum size for a measurable lesion should be twice the slice thickness. An MRI scan is also acceptable in certain situations (e.g., for body scans).

Ultrasound

Ultrasound is not useful in assessment of lesion size and should not be used as a method of measurement. Ultrasound examinations cannot be reproduced in their entirety for independent review at a later date and, because they are operator dependent, it cannot be guaranteed that the same technique and measurements will be taken from one assessment to the next. If new lesions are identified by ultrasound in the course of the study, confirmation by CT or MRI is advised. If there is concern about radiation exposure with CT, MRI may be used instead of CT in selected instances.

Cytology, Histology

These techniques can be used to differentiate between PR and CR in rare cases (e.g., residual lesions in tumour types such as germ cell tumours, where known residual benign tumours can remain) from PD.

10.2. Appendix 2: CYP3A Inhibitors, Inducers, and Substrates

10.2.1. Medications or Foods Known to Inhibit CYP3A

The following list provides medications or foods known to induce or inhibit CYP3A activity. Note that this is not a comprehensive list of all medications or foods which may modulate CYP3A activity. Additional information can be found at:

<http://www.fda.gov/Drugs/DevelopmentApprovalProcess/DevelopmentResources/DrugInteractionsLabeling/ucm080499.htm>

Note: Subjects receiving duvelisib are prohibited from concomitant use of medications or foods that are known to be strong inhibitors or inducers of CYP3A.

Table 20: Classification of In Vivo Inhibitors of CYP3A

Strong Inhibitors ¹	Moderate inhibitors ²	Weak inhibitors ³
Boceprevir, clarithromycin, conivaptan, grapefruit juice ⁴ , indinavir, itraconazole, ketoconazole, lopinavir/ritonavir, mibepradil ⁵ nefazodone, neflifavir, posaconazole, ritonavir, saquinavir, telaprevir, telithromycin, voriconazole	Amprenavir, aprepitant, atazanavir, ciprofloxacin, darunavir/ritonavir, diltiazem, erythromycin, fluconazole, fosamprenavir, grapefruit juice ⁴ , imatinib, verapamil	Alprazolam, amiodarone, amlodipine, atorvastatin, bicalutamide, cilostazol, cimetidine, cyclosporine, fluoxetine, fluvoxamine, ginkgo ⁶ , goldenseal ⁶ , isoniazid, nilotinib, oral contraceptives, ranitidine, ranolazine, tipranavir/ritonavir, zileuton

Abbreviations: AUC: area under the curve; CL: clearance; CYP: Cytochrome P450; US: United States.

1. A strong inhibitor for a specific CYP is defined as an inhibitor that increases the AUC of a substrate for that CYP by ≥ 5 -fold or $> 80\%$ decrease in CL.
2. A moderate inhibitor for a specific CYP is defined as an inhibitor that increases the AUC of a sensitive substrate for that CYP by < 5 -fold but ≥ 2 -fold or 50 to 80% decrease in CL.
3. A weak inhibitor for a specific CYP is defined as an inhibitor that increases the AUC of a sensitive substrate for that CYP by < 2 -fold but ≥ 5 -fold or 20 to 50% decrease in CL.
4. The effect of grapefruit juice varies widely among brands and is concentration-, dose-, and preparation-dependent. Studies have shown that it can be classified as a “strong CYP3A inhibitor” when a certain preparation was used (e.g., high dose, double strength) or as a “moderate CYP3A inhibitor” when another preparation was used (e.g., low dose, single strength).
5. Withdrawn from the US market because of safety reasons.
6. Herbal product.

10.2.2. Medications Known to Induce CYP3A

Please discuss use of weak or moderate CYP3A inhibitors and inducers with the Medical Monitor.

Table 21: Classification of In Vivo Inducers of CYP3A

Strong Inducers $\geq 80\%$ decrease in AUC	Moderate Inducers 50-80% decrease in AUC	Weak Inducers 20-50% decrease in AUC
Avasimibe ¹ , carbamazepine, phenytoin, rifampin, St. John's Wort ^{2,3}	Bosentan, efavirenz, etravirine, modafinil, nafcillin	Amprenavir, aprepitant, armodafinil, Echinacea ³ , pioglitazone, prednisone, rufinamide

Abbreviations: AUC: area under the curve; CYP3A: cytochrome P450 3A.

1. Not a marketed drug.
2. The effect of St. John's Wort varies widely and is preparation-dependent.
3. Herbal product.

10.2.3. Medications Known to Be CYP3A Substrates

Known sensitive CYP3A substrates and CYP3A substrates with a narrow therapeutic range are listed in [Table 22](#). Consider finding an alternative drug that is not a substrate of CYP3A4.

Additional information can be found at:

<https://drug-interactions.medicine.iu.edu/main-table.aspx>

<http://www.pharmacytimes.com/issue/pharmacy/2008/2008-09/2008-09-8687>

Table 22: Cytochrome P450 3A (CYP3A) Substrates

Sensitive CYP3A Substrates	
budesonide buspirone eplerenone eletriptan felodipine fluticasone lovastatin	midazolam saquinavir sildenafil simvastatin triazolam vardenafil
CYP3A Substrates with a Narrow Therapeutic Range	
alfentanil astemizole cisapride cyclosporine diergotamine ergotamine	fentanyl pimozide quinidine sirolimus tacrolimus terfenadine

10.3. Appendix 3: Clinical Laboratory Tests

- The tests detailed in [Table 23](#) will be performed by the local laboratory. The timing and frequency are detailed in the SoA [Table 1](#) and [Table 3](#).
- Protocol-specific requirements for inclusion or exclusion of subjects are detailed in Section [5](#).
- Additional tests may be performed at any time during the study as determined necessary by the Investigator or required by local regulations.
- Investigators must document their review of each laboratory safety report.
- The results of each test must be entered in the CRF.

Table 23: Protocol-required Safety Laboratory Assessments

Laboratory Assessments ^a	Parameters			
Hematology	Platelet Count	RBC Indices: Mean corpuscular volume Mean corpuscular hemoglobin %Reticulocytes	White blood cell count with Differential: Neutrophils Lymphocytes Monocytes Eosinophils Basophils	
	Red blood cell (RBC) Count			
	Hemoglobin			
	Hematocrit			
Clinical Chemistry ¹	Blood urea nitrogen	Potassium	Aspartate Aminotransferase (AST)/ Serum Glutamic-Oxaloacetic Transaminase (SGOT)	Total and direct bilirubin
	Creatinine	Sodium	Alanine Aminotransferase (ALT)/ Serum Glutamic-Pyruvic Transaminase (SGPT)	Total Protein
	Glucose (fasting)	Calcium	Alkaline phosphatase (ALP)	Lactate dehydrogenase (LDH)
Routine Urinalysis	
 • Specific gravity • pH, glucose, protein, blood, ketones, bilirubin, urobilinogen, nitrite, leukocyte esterase by dipstick. If positive, quantitative analysis is needed if not previously noted as part of medical history. • Microscopic examination (if blood or protein is abnormal) 			

Laboratory Assessments ^a	Parameters
Pregnancy	
 Highly sensitive serum/urine human chorionic gonadotropin (hCG) pregnancy test (as needed for women of childbearing potential)²
Other Screening Tests	
 Viral screening: serology (hepatitis B surface antigen [HBsAg], hepatitis B core antibody [HBcAb], hepatitis C virus antibody [HVCAb], Epstein-Barr virus [EBV] antibody, human immunodeficiency virus [HIV] antibody); HPV testing (if status not available at Screening), cytomegalovirus (CMV) via serology, or viral load detection via polymerase chain reaction (PCR). Subjects with a negative HBsAg and positive HBcAb require an undetectable/negative hepatitis B DNA test (e.g., PCR test) to be dosed. 
 HIV testing is required for subjects without documentation of a prior negative test result from within the last 9 months. Results will be analyzed locally and will not be captured in the study database. Only subjects with negative results will be eligible to begin study intervention. Coagulation tests: prothrombin time (PT), activated partial thromboplastin time (aPTT), and international normalized ratio (INR) C-reactive protein^b Triiodothyronine (T3), free thyroxine (FT4), and thyroid-stimulating hormone (TSH) Food and Drug Administration (FDA)-approved PD-L1 testing is required for indications specified in the current pembrolizumab prescribing information (Keytruda 2019), unless results are already available. Information on FDA-approved tests is available at: http://www.fda.gov/CompanionDiagnostics.

NOTES:

- Details of liver chemistry stopping criteria and required actions and follow-up assessments after liver stopping or monitoring event are provided in [Table 12](#) for duvelisib and in [Table 13](#) for pembrolizumab. All liver-related SAEs must be reported as described in Section [8.4.3](#).
- A serum pregnancy test must be performed within 7 days of the first dose. At subsequent time points, serum testing is preferred but urine testing is allowed if a blood draw for other assessments is not performed. A positive urine test result must be confirmed by a serum test.

^a See Section [8.2.4](#) for guidance on repeating/recording laboratory tests with values that are considered clinically significant or that require a change in subject management.

^b Also obtain when Grade ≥ 2 diarrhea, any grade colitis, or any grade immune-mediated toxicity (e.g., pneumonitis, colitis, hepatitis, endocrinopathies, nephritis/renal dysfunction, cutaneous adverse reactions, encephalitis) occurs.

10.4. Appendix 4: Contraception Guidance

The effects of duvelisib on conception, pregnancy, and lactation are unknown. Every woman of childbearing potential (WCBP) and male subjects with a partner who is a WCBP must use contraception as described below. A woman is considered to be a WCBP after menarche and until becoming postmenopausal (i.e., > 55 years and postmenopausal for at least 1 year), unless permanently sterile.

At Screening, all male and female subjects of reproductive potential (i.e., not surgically sterile or female subjects who are not postmenopausal) must agree to use a highly effective method of contraception (see Section 10.4.1) for the duration of the study interventions, and for at least 4 months after the last dose of study interventions. Male subjects must also refrain from donating sperm during their participation in the study and for at least 4 months after the last dose of study interventions.

The use of contraceptive methods is not required if the male subject or the male partner (of the female subject) has a documented history of a vasectomy or if the female subject or the female partner (of the male subject) has a documented history of bilateral oophorectomy, hysterectomy, or tubal ligation, or if she is > 55 years of age and postmenopausal for at least 1 year.

See Section 8.4.9 for requirements for pregnancy reporting.

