 - Total bilirubin level $\leq 1.5 \times$ ULN (exception: subjects with Gilbert's Syndrome may have a bilirubin level $> 1.5 \times$ ULN)
 - Aspartate aminotransaminase (AST)/serum glutamic-oxaloacetic transaminase (SGOT) and alanine aminotransferase (ALT)/serum pyruvic transaminase (SGPT) levels $\leq 2.5 \times$ ULN or $\leq 5 \times$ ULN in subjects with liver metastases
10. Must have an international normalized ratio (INR) or prothrombin time (PT) and activated partial thromboplastin time (aPTT) $\leq 1.5 \times$ ULN, unless subject is receiving anticoagulant therapy in which case PT or aPTT must be within therapeutic range of intended use of anticoagulants

11. Must have an Eastern Cooperative Oncology Group (ECOG) performance status ≤ 1
12. For male and female subjects of reproductive potential (i.e., not surgically sterile or female subjects who are not postmenopausal), must be willing to use a highly effective method of contraception (see Section 10.4) for the duration of the study interventions and for at least 4 months after the last dose of study interventions
13. Must have a negative serum human chorionic gonadotropin (hCG) pregnancy test result within 7 days before the first dose of duvelisib if the subject is a woman of childbearing potential (WCBP)
14. Must provide signed and dated institutional review board (IRB)/independent ethics committee (IEC) -approved informed consent form (ICF) before any study-specific screening procedures are performed

Exclusion Criteria

Subjects will be excluded from the study if they meet any of the following criteria:

1. Have disease that is suitable for local therapy administered with curative intent
2. Have been previously treated with 3 or more systemic regimens given for recurrent and/or metastatic disease
3. Have received anticancer treatment, major surgery, or any investigational drug within 30 days or 5 half-lives, whichever is shorter, before the first dose of duvelisib
4. Have received radiation therapy within 14 days before the first dose of duvelisib in this study, including, in addition (if necessary), the timeframe for resolution of any actual or anticipated toxicities from such radiation. Palliative radiation therapy is allowed if > 7 days before the first dose of duvelisib and any toxicity is \leq Grade 1.
5. Have received prior radiation therapy to $> 25\%$ of bone marrow-bearing areas

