 - Total bilirubin level $\leq 1.5 \times$ ULN (exception: subjects with Gilbert's Syndrome may have a bilirubin level $> 1.5 \times$ ULN)
 - AST/serum glutamic-oxaloacetic transaminase (SGOT) and ALT/serum pyruvic transaminase (SGPT) levels $\leq 2.5 \times$ ULN or $\leq 5 \times$ ULN in subjects with liver metastases
- 10. Must have international ratio (INR) or prothrombin time (PT) and activated partial thromboplastin time (aPTT) $\leq 1.5 \times$ ULN, unless subject is receiving anticoagulant therapy in which case PT or aPTT must be within therapeutic range of intended use of anticoagulants
- 11. Must have an Eastern Cooperative Oncology Group (ECOG) performance status ≤ 1
- 12. For male and female subjects of reproductive potential (i.e., not surgically sterile or female subjects who are not postmenopausal), must be willing to use a highly effective method of contraception (see Section 10.4) for the duration of the study interventions and for at least 4 months after the last dose of study interventions
- 13. Must have a negative serum human chorionic gonadotropin (hCG) pregnancy test result within 7 days before first dose of duvelisib if the subject is a woman of childbearing potential (WCBP) (defined in Section 10.4)
- 14. Must provide signed and dated institutional review board (IRB)/independent ethics committee (IEC)-approved informed consent form (ICF) before any study-specific screening procedures are performed

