5.3. Lifestyle Considerations

Male and female subjects of reproductive potential (i.e., not surgically sterile or female subjects who are not postmenopausal) must use highly effective contraception for the duration of the study interventions and for at least 4 months after the last dose of study interventions. Please see Section 10.4 for detailed contraceptive requirements.

Subjects should be advised to use appropriate protective measures to minimize exposure to direct sunlight or UV light sources during the treatment period and for at least 30 days after the last dose of duvelisib. Please see the duvelisib IB for additional details on the potential for phototoxicity.

Subjects should refrain from consumption of grapefruit juice and St. John's Wort, and other foods and herbal products that are strong inhibitors or inducers of CYP3A during treatment with duvelisib. Please see Section 6.5.2 for additional information on restrictions on the use of CYP 3A inhibitors, inducers, and substrates, and Section 10.2 for lists of CYP3A inhibitors, inducers, and substrates. The duvelisib IB contains additional details on potential interactions with foods.

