8.4.9. Pregnancy

Any pregnancy must be reported to the Sponsor or designee within 24 hours of the Investigator's knowledge of the pregnancy using a Pregnancy Report Form.

Pregnancy per se is not considered an AE unless there is cause to believe that the study interventions may have interfered with the effectiveness of a contraceptive medication or if the outcome of the pregnancy meets SAE criteria (miscarriage or congenital anomaly/birth defect, etc.), in which case it should be reported in the same manner and timelines as an SAE. In addition, any infant death or congenital anomaly occurring after 30 days that the Investigator suspects is related to the in-utero exposure to the study interventions should also be reported as an SAE. Hospitalization for normal delivery of a healthy newborn is not an SAE.

Since duvelisib and pembrolizumab have not been evaluated in pregnant or nursing women, the treatment of pregnant women or WCBP who are not using highly effective contraception is contraindicated (see Table 23 and Section 10.4 for instructions on pregnancy testing and contraception).

Pregnancies occurring in subjects or partners of male subjects during the study intervention period and until 30 days after the subject's last dose of study interventions are considered immediately reportable events. If a pregnancy occurs in a subject, study interventions must be discontinued immediately. The pregnant woman should be referred to an obstetrician/gynecologist experienced in reproductive toxicity for further evaluation and counseling. The Investigator will observe the pregnant woman until completion of the pregnancy and must notify the Sponsor of the outcome within 24 hours of the Investigator's knowledge of the pregnancy outcome using a Pregnancy Outcome Form. This notification includes pregnancies resulting in live, "normal" births.

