10.4.1. Highly Effective Methods of Contraception

Methods that can achieve a failure rate of less than 1% per year when used consistently and correctly are considered as highly effective birth control methods. Such methods include:

- combined (estrogen and progestogen containing) hormonal contraception associated with inhibition of ovulation^a:
 - oral
 - intravaginal
 - transdermal
- progestogen-only hormonal contraception associated with inhibition of ovulation^a:
 - oral
 - injectable
 - implantable^b
- intrauterine device (IUD)^b
- intrauterine hormone-releasing system (IUS)^b
- bilateral tubal occlusion^b
- vasectomized partner^{b,c}
- sexual abstinence^d

^a Hormonal contraception may be susceptible to interaction with the Investigational Medicinal Product (IMP), which may reduce the efficacy of the contraception method.

^bThis method of contraception should preferably be used, in particular when contraception is introduced as a result of participation in the clinical study.

^cVasectomized partner is a highly effective birth control method provided that partner is the sole sexual partner of the WCBP trial participant and that the vasectomized partner has received medical assessment of the surgical success.

^dSexual abstinence is considered a highly effective method only if defined as refraining from heterosexual intercourse during the entire period of risk associated with the study treatments. The reliability of sexual abstinence needs to be evaluated in relation to the duration of the clinical study and the preferred and usual lifestyle of the subject.

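### Section 10.4 waives contraception on a partner's documented vasectomy alone, while Section 10.4.1 also asks for medically assessed success and sole-partner status

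*Combined protocol and SAP*

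**What the plan says.** Section 10.4 requires every WCBP, and every male subject with a WCBP partner, to use contraception, and sends subjects of reproductive potential to Section 10.4.1 for a highly effective method. Its third paragraph then lifts the requirement. Methods are "not required if the male subject or the male partner (of the female subject) has a documented history of a vasectomy", or on certain other grounds such as hysterectomy or tubal ligation. The grounds are alternatives, so a documented vasectomy is enough on its own.

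Section 10.4.1 lists a vasectomized partner among the highly effective methods, but footnote c attaches two conditions. He qualifies "provided that partner is the sole sexual partner of the WCBP trial participant" and on the further condition "that the vasectomized partner has received medical assessment of the surgical success".

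Section 8.4.9 (Pregnancy) adds that "the treatment of pregnant women or WCBP who are not using highly effective contraception is contraindicated".

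**The concern.** For a female subject, the same fact about her partner leads to two different rules. Under the waiver, a record that he had a vasectomy ends her obligation to use any method. Under footnote c, that record alone does not make him an adequate method.

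A site that follows the waiver as written could dose a WCBP whom the protocol's own standard treats as unprotected. Section 2.4.1 names reproductive toxicity as a potential risk of duvelisib, and Section 10.4 says its effects on conception and pregnancy are not known. Treatment may run for up to 24 months, and the contraception requirement continues for at least 4 months after the last dose.

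**Working it through.** No calculation applies; the check is a comparison of texts.

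**1. The two rules for a WCBP's vasectomized partner.**

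| Condition | Section 10.4 waiver | Section 10.4.1, footnote c |
|---|---|---|
| Vasectomy performed | Required (documented history) | Required |
| Surgical success medically assessed | Not stated | Required |
| Sole sexual partner | Not stated | Required |

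The waiver states 0 of footnote c's 2 conditions. The medical assessment is the clearer gap, since a documented operation does not plainly include a check that it worked. The sole-partner gap is weaker, because the waiver speaks of the male partner in the singular and can be read as assuming there is only one.

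**2. Does the partner's vasectomy take her out of the WCBP group?** No. Section 10.4 says "A woman is considered to be a WCBP after menarche and until becoming postmenopausal", with an exception for permanent sterility. Each element describes the woman herself. She remains a WCBP, so Section 8.4.9 still applies to her.

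**3. Does another section settle the matter?** There are five contraception statements outside Section 10.4.

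| Place | Refers to Section 10.4 | States either condition |
|---|---|---|
| Synopsis, inclusion criterion 12 | Yes: "must be willing to use a highly effective method of contraception (see Section 10.4" | No |
| Section 5.1, inclusion criterion 12 | Yes | No |
| Section 5.3, Lifestyle Considerations | Yes: "Please see Section 10.4 for detailed contraceptive requirements" | No |
| Section 6.5.3, Contraception and Pregnancy | Yes | No |
| Section 8.4.9, Pregnancy | Yes | No |

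All 5 return the reader to Section 10.4, and 0 of 5 supply a condition.

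**4. Is this superseded or damaged text?** No. Both passages are current, the summary of changes for Version 2.0 lists no change to contraception, and nothing around either sentence is redacted.

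**5. How far does it reach?** Footnote c concerns only the partner of a WCBP participant. A male subject's own vasectomy is therefore not in conflict with it.

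**The case against.** The strongest reply is that the texts can be read together. Section 10.4.1 sits inside Section 10.4, so footnote c could be taken as the specific rule and the waiver as a loose summary for couples already covered by surgery. Criterion 12 supports the stricter reading: in Section 5.1 it says "subjects of reproductive potential (i.e., not surgically sterile or female subjects who are not postmenopausal), must be willing to use a highly effective method", and a partner's operation does not change her reproductive potential. Section 8.4.9 points the same way, and Section 5 forbids waivers of enrolment criteria. On this view, harm needs a site to read one sentence and ignore the rest.

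This does show that the stricter rule is probably the intended one. It does not remove the conflict. The joint reading is inferred from layout; nothing in the text makes the waiver subject to footnote c. The footnote qualifies a listed method, whereas the waiver says no method is needed, so a site applying it has no reason to reach the footnote. Criterion 12 and Section 8.4.9 themselves refer back to Section 10.4.

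Pregnancy tests at cycle visits, and stopping treatment on pregnancy, limit exposure. They detect a pregnancy and do not prevent one.

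The point about scale stands in full: the documents do not show that any enrolled woman would be affected.

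**Conclusion.** The inconsistency is real, and it is minor. On the words of the protocol, a WCBP can be exempt from contraception under Section 10.4 while her treatment is contraindicated under Section 8.4.9. Confidence is high that the wording differs on medical assessment. It is lower for the sole-partner condition, which depends on how the singular is read.

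The number affected cannot be computed. It would take a WCBP among the 30 planned subjects who has a vasectomized partner, uses no other method, and either has a partner whose operation was never assessed or has another partner as well. The documents give none of these frequencies. The ORR test, the DLT evaluation and every planned analysis are unaffected. This is a cheap improvement in patient protection and should rank below any point that bears on dosing or inference.

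**What to change.** Add footnote c's two conditions to the partner clause of the waiver. For example: 'or the male partner of a female subject has a documented vasectomy whose success has been medically assessed, and he is her only sexual partner'. Alternatively, delete the partner clause, so that a vasectomized partner counts only through Section 10.4.1. Leave the clause on a male subject's own vasectomy alone. The five statements elsewhere already refer to Section 10.4 and need no edit.

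The sponsor used a clarification memorandum on 05 June 2020 for the Stage 1 PK draw, and the same route could carry this change, with the text taken into the next amendment if there is one. That memorandum cancelled a blood draw, whereas this would tighten a condition of participation, so the sponsor should check what Section 10.6.1 requires by way of IRB/IEC approval.

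The cost is one clause. It adds no study visits, study tests or subjects. A few women may need to obtain confirmation of the partner's surgical success, which could mean a search of records belonging to someone outside the study, or else use another listed method. Footnote c already asks for that.
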